4.5 SUBJECT RANDOMIZATION AND TREATMENT GROUP ASSIGNMENT

At the Treatment visit, only qualified study subjects (i.e., signed the IRB-approved consent form and confirmed eligible) will be randomly assigned according to a computer-generated 1:1 randomization to receive Ultherapy® treatment using either the Simulines or Standard transducers.

Randomizations will be stratified by site and will use randomly selected blocks of size 4 and 6 and will be generated by an electronic database in a reproducible fashion and will be provided to the site by electronic data capture the point that randomization occurs.

Enrolled subjects will be randomized to one of two treatment groups. Subjects and the study clinician performing efficacy assessments should remain blinded to the assigned treatment group. All randomized subjects will receive a single, dual depth lower face and neck Ultherapy® treatment. Group A will receive treatment with Standard transducers at EL2. The number of treatment lines in each region currently requiring an odd number of lines will be rounded up to an even number for equivalency between Standard and Simulines (e.g. if 15 lines are required in a region on the Standard transducer treatment map then this will be rounded up to 16 lines to match the 16 lines required on the Simulines map). Group B will receive treatment with Simulines transducers at EL2.

Subjects randomized to Group A will receive an Ultherapy® treatment to the lower face and neck with a total minimum pulse count of 672 pulses (+5%) at the 4.5mm and 3.0mm depths using Standard transducers. Energy levels for each transducer will be set to EL2:

- DS 4-4.5 at 0.9J with pitch of 1.5mm and 17 TCP's per line
- DS 7-3.0 at 0.30J with pitch of 1.1mm and 23 TCP's per line

Subjects randomized to Group B will receive a comparable treatment with a total minimum pulse count of 336 pulses (+5%) using the Simulines transducers at the 4.5mm and 3.0mm. Energy levels for each transducer will be set to EL2:

The assigned treatment group should be documented on the appropriate study-specific data form and study log.

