5.3 QUANTITATIVE MEASURES

Submandibular/Submentum quantitative measurements calculated as detailed in **Attachment A**, comparing subjects treated using Simulines versus Standard transducers, will be obtained based on 2D study images obtained at follow-up visits post-treatment compared to baseline.

Comparison of improvement data for overall lifting and tightening of skin as determined by a masked, qualitative assessment of photographs obtained at follow-up visits post-treatment compared to baseline as detailed in **Attachment F**.

Secondary effectiveness will be assessed at baseline and 90 days using the validated, Merz Jawline Grading Scale (MJGS) (**Attachment G**) by independent, masked evaluators using photographs obtained at baseline and the 90-day follow-up visit. The evaluators will be trained and qualified on the MJGS by the sponsor and will remain masked throughout the study. The MJGS is an ordinal scale and ratings will be made based on a “snap-shot” at a single point in time and therefore will not be based on a comparison to a pre-treatment photograph.

The Global Aesthetic Improvement Scale (GAIS) (**Attachments B and C**) will be obtained at all post-treatment time points. The GAIS is a 5-point scale that rates global aesthetic improvement from the pre-treatment appearance. The ratings are worse, no change, improved, much improved, and very much improved. It was validated by [name], et al. for this use. In this study, both live observation and photo review are utilized by the clinician (CGAIS) and subject (SGAIS) in order to assign a score. The CGAIS must be performed by the primary investigator, or a qualified study staff member delegated by the PI. Both the CGAIS and SGAIS should be completed in two steps:

- Based on a live assessment of the subject while referring to the subject’s pre-treatment photographs (subjects should be given a hand mirror for this assessment); and
- Based on a comparison of the subject’s pre-treatment photographs to the current post-treatment photographs.

A validated Numeric Rating Scale (0-10) (**Attachment D**) will be used to record subjects’ pain scores during study treatment. Scores will be obtained for each region treated and for each transducer used.

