6.4.1 ASSESSMENT OF COMPARABILITY OF RANDOMIZED GROUPS AND POOLABILITY OF INVESTIGATIONAL SITES

Summary tables describing the study population will be produced using subjects in the intent-to-treat population by randomized group. The study population will be described in terms of subject disposition, baseline characteristics, and concomitant medications. Subject disposition parameters will include number of subjects enrolled, treated, discontinued, and reasons for discontinuation. Baseline characteristics will include demographics, height, weight, BMI, and medical history.

The primary efficacy endpoint will be summarized by randomized group and investigational site in the observed intent-to-treat subjects. Although enrollment is set at a minimum of 20 subjects per site, if there is some unforeseen event preventing this minimum level of enrollment per site, investigational sites with fewer than 10 subjects will be combined for this purpose. A random center effect and a random center by randomized group (ITT) interaction will be included in the primary statistical model using logistic regression. If the p-value for the interaction term variance component is < 0.15 , the interaction term and the random center effect will be retained in the model and the effect of treatment will be estimated using this model as an additional analysis to the primary objective. If the p-value for the interaction term variance component ≥ 0.15 and the random center effect is < 0.05 , the random center effect alone will be retained in the model and the effect of treatment will be estimated using this model as an additional analysis to the primary objective. If neither is significant, the effect of treatment will not need to be re-estimated using a model that includes random center or center by treatment effects. The study is not powered to find a statistically significant treatment effect if significant center heterogeneity or effect modification is found, the models however, can be used to pool the data to assess the effect of center heterogeneity or effect modification on the estimated treatment effect.

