6.4.3 EFFICACY ANALYSIS

6.4.3.1 PRIMARY EFFICACY ANALYSES

Subjects included in the analysis: All ITT subjects will be included in the analysis.

Endpoint: Subject response is defined as ≥ 20 mm² reduction in 2D submental area from baseline. The left and right side value at baseline will be averaged to result in the 2D submental area at baseline. The left and right side value at 90 days will be averaged to result in the 2D submental area at 90 days. In the event, only either the left or right side data is available, it will be used. Response will be calculated as baseline – 90 days. The evaluator that determines 2D submental area is blinded to follow-up and study group.

Hypothesis:

H₀: The proportion of responders at 90 days as compared to baseline for the test group is inferior as compared to the control group given a non-inferiority margin of δ , $p_{\text{control}} - p_{\text{test}} \geq \delta = 15\%$.

H_a: The proportion of responders at 90 days as compared to baseline for the test group is not inferior as compared to the control group given a non-inferiority margin of δ , $p_{\text{control}} - p_{\text{test}} < \delta = 15\%$

Sample Size Rationale: The sample size calculation assumes 73% response in both randomized groups. Power was set at 80%, one-sided Type I error controlled at 5%, a non-inferiority margin of 15% and PASS 12 Non-inferiority for two independent proportions using the Z-test with unpooled variance was used. The sample size requires 109 subjects per randomized group to have data necessary to calculate the primary endpoint. The total sample size of 218 was corrected for up to 16% attrition to arrive at 260 subjects randomized in the study.

Primary Statistical Analysis: The primary statistical analysis will be conducted using the observed data in the intent-to-treat patients using the Z-test (unpooled) for two independent proportions. Statistical significance is determined using a one-sided $\alpha=0.05$.

Additional Statistical Analysis: If there are intent to treat subjects with missing data, the analysis as specified in Section 6.4.1 Handling of Missing data will be conducted. The analysis in Section 6.4.1 regarding pooling will be conducted as specified in that section. The analysis will be completed for the subset of per protocol patients.

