Endpoint: The proportion of “Improved, correct pre-post selection” out of the total number of responses. The total number of responses includes the number responding “Improved, correct pre-post selection”, “Improved, incorrect pre-post selection” and “No change”.

Statistical Analysis: A repeated measures model will be used to analyze the data from this objective. The dependent variable will be the proportion meeting the endpoint. The independent variables will be study group and day of follow-up. A covariance structure will be used to account for the correlation expected among the repeated observations collected for each subject. The covariance structure that fits the data best, i.e. results in the lowest Schwarz Bayesian Information Criteria (BIC) value all else held constant will be used, among the unstructured, compound symmetric or auto-regressive types. Statistical significance will be determined using a two-sided $\alpha=0.05$.

6.4.3.2.3 Assessment of mean change and ≥ 1 point improvement from baseline to 90 days post treatment on the validated, Merz Jawline Grading Scale (MJGS) by an independent masked evaluator.

Endpoints: Change in MJGS from baseline to 90 days and proportion of subjects with a ≥ 1 point improvement from baseline to 90 days post treatment. Three masked evaluators that will review subject photos and will be blinded to treatment assignment and follow-up.

Statistical analysis: The mean change in MJGS from baseline to 90 days will be compared between study groups using the Two-sample T-test. The proportion of subjects with ≥ 1 point improvement from baseline to 90 days post treatment will be compared using Fisher’s exact test.

6.4.3.2.4 Quantificare 3D imaging of up to 135 study subjects to assess volumetric changes from baseline compared to 90, 180, and 365 days post-treatment.

Endpoints: Change in volume as calculated per the Quantificare 3D imaging system (see Appendix I) from baseline to 90, 180 and 365 days post-treatment. The evaluator that determines Quantificare volume is blinded to follow-up and study group.

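### The jawline-scale mean change is compared without adjusting for the baseline grade already collected, which gives up some precision and leaves the estimate exposed to chance baseline imbalance

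*Combined protocol and SAP*

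**What the plan says.** All references are to the combined protocol and SAP.

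- **Analysis (6.4.3.2.3).** "The mean change in MJGS from baseline to 90 days will be compared between study groups using the Two-sample T-test". For the companion responder endpoint, the proportions improving by at least one point "post treatment will be compared using Fisher’s exact test". Neither analysis has a covariate, and the section names tests only, with no confidence interval.
- **Baseline grade (5.3 and the Jawline Scale row of Table 3.1-1).** "Secondary effectiveness will be assessed at baseline and 90 days using the validated, Merz Jawline Grading Scale (MJGS"), rated by masked evaluators from photographs. "The MJGS is an ordinal scale and ratings will be made based on a" view at one time point, not a comparison with the pre-treatment photograph. Section 6.4.3.2.3 adds that three evaluators are blinded to treatment and to follow-up.
- **Allocation (4.5).** Subjects are "randomly assigned according to a computer-generated 1:1 randomization". "Randomizations will be stratified by site and will use randomly selected blocks of size 4 and 6". Baseline MJGS is not a stratification factor.
- **Baseline tables (6.4.1).** "Baseline characteristics will include demographics, height, weight, BMI, and medical history". MJGS is not in that list.
- **Other analysis text.** Section 6.4 allows alternative summaries, nonparametric methods or transformations. The centre model in 6.4.1 belongs to the primary endpoint and contains centre and treatment terms only. Neither brings in baseline MJGS.
- **Status (6.4.3.2).** Secondary endpoints are supportive and are not meant to carry additional claims.

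**The concern.** Each photograph is graded on its own, so rater error enters the baseline grade and the Day-90 grade separately and pulls the correlation between them below 1. Subtracting baseline from follow-up assumes that a subject who starts one grade higher will, without any treatment difference, finish one grade higher. If the true slope is smaller, the change score over-corrects.

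Two things follow. The estimated difference between arms is noisier than the same data allow. And if one arm happens to be graded worse at baseline, it tends to show more improvement whatever the transducer. Stratification by site does nothing to limit such an imbalance, and the listed baseline characteristics would not show it. What is at stake is the precision and the reading of one masked Day-90 comparison, not the decision on non-inferiority.

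**Working it through.** **Inputs.** Allocation is 1:1 (4.5). For the number per arm I borrow the primary-endpoint figure in 6.4.3.1: "The sample size requires 109 subjects per randomized group to have data necessary to calculate the primary endpoint". The documents give no MJGS correlation, SD, effect size or power, so ρ and s1/s0 are assumed over a range.

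**1. The plan's own figure.** With 73% response in both arms, a 15% margin, one-sided 5%, 80% power and unpooled variance:

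n = (1.6449 + 0.8416)² × 2 × 0.73 × 0.27 / 0.15² = 108.3, rounded up to 109 per arm, 218 in total. Then 218/0.84 = 259.5, rounded up to 260. This reproduces. It concerns the primary endpoint only.

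**2. Variance per subject (large-sample).**

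- Change score: s0² + s1² − 2ρ·s0·s1
- Baseline-adjusted: s1²(1 − ρ²)
- The first minus the second is (s0 − ρ·s1)². It is never negative, and it is zero only when ρ·s1/s0 = 1.

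With s0 = s1 = s these become 2s²(1 − ρ) and s²(1 − ρ)(1 + ρ), so adjusted/change = (1 + ρ)/2.

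**3. Effect of a baseline imbalance d.** The change-score difference carries (ρ·s1/s0 − 1)·d, which is −(1 − ρ)·d with equal SDs. At 109 per arm the SE of the baseline difference is √(2/109) = 0.135 SD, so an imbalance of 1.96 SE is 0.265 SD.

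**4. Results, equal SDs, 109 per arm, in baseline-SD units.** For example, at ρ = 0.5 the 95% half-width is 1.96 × √(2 × 1.00/109) = 0.265 for change and 1.96 × √(2 × 0.75/109) = 0.230 adjusted.

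| ρ | Variance cut | SE ratio | Half-width, change | Half-width, adjusted | Shift from a 1.96-SE imbalance |
|---|---|---|---|---|---|
| 0.5 | 25% | 0.866 | 0.265 | 0.230 | 0.133 |
| 0.7 | 15% | 0.922 | 0.206 | 0.190 | 0.080 |
| 0.8 | 10% | 0.949 | 0.168 | 0.159 | 0.053 |
| 0.9 | 5% | 0.975 | 0.119 | 0.116 | 0.027 |

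The shift is in size only; its sign is opposite to that of the imbalance.

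**5. Unequal SDs.** Adjusted/change variance ratio:

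| s1/s0 | ρ = 0.5 | ρ = 0.7 | ρ = 0.8 | ρ = 0.9 |
|---|---|---|---|---|
| 0.8 | 0.571 | 0.628 | 0.640 | 0.608 |
| 1.2 | 0.871 | 0.966 | 0.997 | 0.977 |

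At s1/s0 = 1.2 and ρ = 0.8, ρ·s1/s0 = 0.96 and almost nothing is gained. At ρ = 0.9 it is 1.08, so the carried fraction is +0.08 and its sign is no longer reversed.

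**6. Check on a coarse scale.** Simulation with no treatment effect, an assumed five-grade rounded scale, 109 per arm, 2,000 runs, and correlation before rounding of 0.5, 0.7 and 0.8:

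- Adjusted/change SE ratio: 0.85, 0.90, 0.93.
- Correlation of the change-score estimate with the baseline imbalance: −0.53, −0.46, −0.39. For the adjusted estimate it was within 0.02 of zero, to two decimals.
- Type I error at a two-sided 5% level: between 4.3% and 5.4% for both methods.

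**The case against.** The strongest reply is that nothing here is an error. Randomisation makes regression to the mean act equally on both arms in expectation, so the T-test on change is unbiased over repeated randomisations and holds its level. That stands. The change score also removes much of any imbalance already; at ρ = 0.8 with equal SDs only a fifth gets through. That stands too.

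The gain may be small. Section 6.4.3.2.3 does not say how the three evaluators' grades are combined. If they are averaged, rater error falls, ρ rises, and the saving moves towards the 10% or 5% rows. Nor should the saving be turned into a firm power figure. A difference that the T-test would detect with 80% power would be detected with about 90% at ρ = 0.5 or 84% at ρ = 0.8, but the plan states no MJGS effect or power; its 80% belongs to the primary endpoint.

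A reader might infer that the lost precision favours the Simulines arm because this is a non-inferiority trial. The documents do not support that. Non-inferiority is decided only on the primary responder endpoint against the 15% margin (6.2 and 6.4.3.1). MJGS has no margin, and nothing says that a non-significant T-test will be read as similarity. If MJGS were judged by a confidence interval against a margin, lower precision would make non-inferiority harder to show. Nor is a planned interval being widened, since the section specifies none; the loss is in the precision of the estimated difference.

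None of this is a reason to leave the baseline grade out, since it is already collected and the large-sample variance cannot rise.

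**Conclusion.** The point holds as a minor improvement. The planned T-test is valid but does not make full use of the baseline grade. With equal SDs, adjustment lowers the variance of the difference by 25% to 5% for ρ from 0.5 to 0.9. It also removes, to a close approximation, the dependence on chance baseline imbalance, which at 109 per arm could shift the change-score difference by 0.13 SD (ρ = 0.5) to 0.03 SD (ρ = 0.9) for an imbalance of 1.96 SE.

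These sizes rest on assumed ρ, on the equal-SD assumption, and on the primary endpoint's 109 per arm. The gain all but disappears when ρ·s1/s0 is near 1. Study success does not depend on this endpoint, and no direction of advantage to either transducer follows.

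**What to change.** In 6.4.3.2.3, replace the T-test on change with a linear model of Day-90 MJGS (or of change, which gives the same treatment estimate once baseline is in the model). Include study group, baseline MJGS and, as the randomisation stratum, site. Report the adjusted difference between groups with its 95% confidence interval. The T-test may stay as a descriptive check, and Fisher's exact test for the responder proportion can stand as written.

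The cost is about one sentence of SAP text, best fixed before unblinding so that adjustment is not a post-hoc choice. It needs no new data, visits, ratings or subjects. With up to eight sites, the site term uses at most 8 − 1 = 7 degrees of freedom, which is negligible with about 218 evaluable subjects.

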6.5 SAFETY ANALYSES

The safety analysis will be performed using subjects in the intent-to-treat population. The safety outcome will be incidence of all treatment-emergent adverse events, where “treatment-emergent” is defined as beginning or worsening after treatment initiation. Incidence of device-related adverse events will also be summarized separately.

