5.1 STUDY TREATMENT

5.1.1 TRANSDUCERS

Two types of the Standard transducers with Energy Level 2 (EL2) will be used during this trial:

1. 4 MHz with a 4.5mm focal depth
2. 7 MHz with a 3.0mm focal depth

Two types of the Simulines transducers with EL2 will also be used:

1. 4MHz with a 4.5mm focal depth
2. 4MHz with a 3.0mm focal depth.

The region to be treated and the transducer used must be appropriately selected on the Ulthera® system and thus recorded on the Treatment Parameter System Record. The Ulthera system will default to EL2 with the study sites instructed not to adjust the energy level.

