6.3 ANALYSIS POPULATIONS

The intent-to-treat population is defined as all subjects who were randomized with study group defined by the randomization.

The per-protocol population is defined as the subset of ITT subjects who:

- met the major inclusion and exclusion criteria
- received within +/- 5% of the total lines per protocol for the randomized treatment
- had in-office follow-up visits either in window or out of window but within 7 days of window open/close
- had primary endpoint data available with acceptable photographic quality as determined by the 3rd party evaluator
- did not have any major protocol violations

The major inclusion/exclusion criteria include age 30 to 70 years, inclusion #3, #4, #8, adherence to photography procedures (i.e., removal of jewelry and makeup), exclusion #1, #7, #8, #11 - #15, #19, #21, #24, #27-#29.

The major protocol violations are defined as:

- use of any other pre-medication for pain besides ibuprofen and administration of ibuprofen less than 45 minutes or more than 135 minutes prior to initiation of study treatment
- any change to the energy level of the device during treatment
- accidental unblinding of investigators completing blinded assessments or subjects during treatment

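### Safety is analysed in all randomised subjects by assigned arm, so untreated subjects stay in the denominator and a wrong-device event is charged to the wrong transducer; the effect is probably small and cheap to remove

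*Combined protocol and SAP*

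**What the plan says.** - **Analysis set.** Section 6.5: "The safety analysis will be performed using subjects in the intent-to-treat population".
- **Who that is, and how grouped.** Section 6.3: "The intent-to-treat population is defined as all subjects who were randomized with study group defined by the randomization". Grouping by assigned arm comes from this definition; Section 6.5 does not state it separately.
- **Outcome.** Section 6.5 reports the incidence of treatment-emergent adverse events, where treatment-emergent "is defined as beginning or worsening after treatment initiation", and summarises device-related events separately.
- **Other populations.** The only other one is per-protocol: "The per-protocol population is defined as the subset of ITT subjects who" meet a list of conditions, among them that they "received within +/- 5% of the total lines per protocol for the randomized treatment". No safety, treated or as-treated set is defined.
- **Timing.** Section 4.5: "At the Treatment visit, only qualified study subjects" are randomised, and "All randomized subjects will receive a single, dual depth lower face and neck Ultherapy® treatment".
- **Exposure record.** Section 5.1.1 requires that the region and the transducer "must be appropriately selected on the Ulthera® system and thus recorded on the Treatment Parameter System Record".

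**The concern.** The numerator depends on treatment having started; the denominator does not. If anyone is randomised and then not treated, that arm's incidence is understated. If anyone assigned to one transducer type is treated with the other, any resulting event is reported under the device that was not used. This is most awkward for the device-related summary, where the investigator has judged a particular device to be the cause.

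A mix-up is not far-fetched. Each session uses two transducers in turn, 4.5 mm and then 3.0 mm (Section 5.1.4). The two 4.5 mm models differ in name by one letter, DS 4-4.5 and DS 4-4.5S (Table 1.4-1), and Section 1.7.2 drops that letter when naming the Simulines models. The per-protocol definition already provides for departures from the randomised treatment on the efficacy side. Safety has no matching rule.

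At stake is the safety half of the objective in Section 6.1, that Simulines is no less safe than Standard. Because Section 6.5 gives only incidence summaries, that half is read directly from the table, so the events should appear under the device that was applied.

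**Working it through.** **Inputs.** Section 6.4.3.1: 73% response in both groups, margin 15%, one-sided alpha 5%, power 80%, unpooled Z-test, 16% attrition, 260 randomised. Section 4.5: 1:1 allocation. The documents give no adverse event rate, no never-treated rate and no wrong-device rate; all of these below are assumptions, shown over a range.

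**The plan's own figures.** n per group = (1.645 + 0.842)² × 2 × 0.73 × 0.27 / 0.15² = 108.3, rounded up to 109. Then 218 / (1 − 0.16) = 259.5, rounded up to 260. Both reproduce. At 1:1 this gives 260 / 2 = 130 per arm, used below. The point does not otherwise depend on these figures.

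**Dilution.** With u never-treated subjects in an arm and true incidence p among the treated, the ITT incidence is p × (130 − u) / 130. Each such subject lowers it by a relative 1/130 = 0.77%.

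| True incidence | u = 2 | u = 5 | u = 10 |
|---|---|---|---|
| 5% | 4.92% | 4.81% | 4.62% |
| 10% | 9.85% | 9.62% | 9.23% |
| 20% | 19.69% | 19.23% | 18.46% |

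**Direction of dilution.** Assume true rates of 10% (Simulines) and 4% (Standard), a difference of 6.0 points.
- Ten untreated, all Simulines: 10% × 120/130 = 9.2%; difference 9.2 − 4.0 = 5.2 points.
- Ten untreated, all Standard: 4% × 120/130 = 3.7%; difference 10.0 − 3.7 = 6.3 points.

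The first flatters Simulines and the second counts against it.

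**Mix-ups in both directions.** With x subjects per arm treated with the other type, the Simulines arm shows ((130 − x) × pS + x × pC) / 130 and the Standard arm shows the mirror image. The difference becomes (pS − pC) × (1 − 2x/130), so each swapped pair shrinks it by a relative 2/130 = 1.5%.

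| True rates (Simulines, Standard) | True difference | x = 1 | x = 5 | x = 13 |
|---|---|---|---|---|
| 5%, 2% | 3.0 points | 2.95 | 2.77 | 2.40 |
| 10%, 5% | 5.0 points | 4.92 | 4.62 | 4.00 |
| 20%, 10% | 10.0 points | 9.85 | 9.23 | 8.00 |

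At 10% and 4% with x = 5: (0.10 × 125 + 0.04 × 5) / 130 = 9.77% against (0.04 × 125 + 0.10 × 5) / 130 = 4.23%, a difference of 5.5 points.

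**One rare event.** Suppose the only case of some event occurs in a subject assigned Standard but treated with Simulines.
- As planned: Simulines 0/130, Standard 1/130 (0.77%).
- By device received: Simulines 1/131 (0.76%), Standard 0/129.

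The percentages hardly move, but the event changes column.

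**The case against.** The strongest reply is that conduct will make the populations almost identical. Randomisation takes place at the treatment visit, in subjects already confirmed eligible, and treatment is a single session. The synopsis sizes the trial in subjects randomised and treated. A subject who stops because treatment is not tolerated has been treated and belongs in either denominator. Wrong-device use should be rare and visible: the console records the transducer, and the arms differ twofold in minimum pulse count (672 against 336). Section 6.4.1 reports the number treated, so a gap would show. All of this stands, and it is why the effect is likely to be small. It does not change what the stated rule would do with an untreated or wrong-device subject.

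Three stronger readings are tempting, and the documents do not support them.
- *The choice always favours Simulines when Simulines is worse.* This holds for two-way mix-ups. It fails for dilution, which can widen the difference, as the 6.3-point case shows.
- *It could produce a false claim of safety non-inferiority.* Section 6.2 ties study success to the primary efficacy objective alone, and Section 6.5 sets no safety hypothesis, margin or test. Only a descriptive table is affected.
- *The 16% attrition allowance implies many untreated subjects.* Section 6.4.3.1 uses it to cover missing primary endpoint data, not failure to treat.

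**Conclusion.** The point holds as a defect in the stated rule with a probably small numerical effect. Sections 6.5 and 6.3 read together put treatment-emergent and device-related events on a randomised denominator grouped by assignment, and nothing elsewhere corrects this. With 130 per arm, each untreated subject costs that arm a relative 0.77% and each swapped pair costs the difference a relative 1.5%. Differences of half a point or more need assumptions, such as five mix-ups each way at rates of 10% and 4%, for which the documents give no evidence. The practical exposure is a rare event, where a single case can appear under the wrong device. If every randomised subject is treated wholly as assigned, the present and proposed analyses give the same result. The change is worth making because it replaces a stated rule with a better one at almost no cost, not because the safety conclusion is shown to be at risk.

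**What to change.** In Section 6.3, add a Safety population: *all randomised subjects who received at least one treatment pulse, grouped by the transducer type actually used according to the Treatment Parameter System Record*. List separately, with their events, any subject exposed to both types and any subject whose actual and assigned groups differ. Do not assign a mixed-exposure subject to Simulines on the strength of any single Simulines pulse: that would charge Simulines with events from a treatment delivered almost wholly with Standard, which is the same misattribution in reverse.

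In Section 6.5, use the Safety population for treatment-emergent and device-related events, and keep the ITT version as supportive. Settle the rule before unblinding, so that which device an event belongs to is not argued afterwards.

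Cost: a few sentences in Section 6 and one derived variable from records already collected. The 260 subjects, the power and every efficacy analysis are unchanged.
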